Type I error. The significance level will be 0.025 for the 1-tailed noninferiority tests for the primary outcome and for each set of the secondary outcomes, and 0.05 for each of the 2-tailed superiority tests for tertiary outcomes (i.e., no adjustment for multiple testing for tertiary outcomes).

Our primary hypothesis is that HES 130/0.4 is noninferior to standard care effects on **mean urinary NGAL** measured within one hour of arrival to ICU and 24 following completion of surgery. We a priori define the noninferiority delta for urinary NGAL as a ratio of geometric means (since NGAL data are expected to be lognormal) of 1.15, for an effective delta of 15% of the control group mean. [Note: for this and other outcomes, if the data are non-normal, a log-transformation will be attempted and the treatment effect (if normal on the log-scale) will be summarized as the ratio of geometric means, equivalent to the difference in means of the log-transformed data.] As noted below under “Continuous outcomes measured over time (Primary and Secondary Aims)”, we will assess the treatment effect for the primary outcome in the context of a linear mixed model which allows us to simultaneously assess the effect across the collapsed time points if there is no group-time interaction, or else at specific times if there is an interaction detected. We will conduct tests for noninferiority using treatment effect estimates from the linear mixed model and applying 1-tailed t-tests for noninferiority as described in Mascha and Sessler (2011) [Mascha EJ, Sessler DI: Statistical grand rounds: Equivalence and noninferiority testing for regression models and repeated measures designs. Anesth Analg 2011; 112: 678–87], and with t-statistic as follows:

$$T_{NI} = \frac{\hat{\beta}_1 + \delta}{SE_{\hat{\beta}_1}}, \text{ where } \hat{\beta}_1 \text{ is the estimated treatment effect with standard error}$$

$SE_{\hat{\beta}_1}$ and noninferiority delta of δ .

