In Secondary Aim 1 – **kidney function** – we will assess noninferiority of HES to albumin on each of urinary concentration of II-18 and acute kidney injury as classified by RIFLE criteria, using statistical methods reported below under continuous (urinary concentration of II-18) and ordinal (RIFLE criteria) outcomes. These will be 1-tailed tests for noninferiority, using a noninferiority delta of 15% of the mean (or a ratio of geometric means of 1.15, if data are found to be log-normally distributed) for urinary concentration of II-18 and a noninferiority delta of 1.15 for the odds ratio assessing the effect of HES 130/0.04 on the ordinal RIFLE outcome. The noninferiority delta of 1.15 corresponds to a 15% higher odds of having a worse RIFLE score with HES 130/0.04 versus standard, and is roughly analogous to the 15% difference utilized for the continuous outcomes (urinary NGAL and II-18). A Bonferroni correction will be made to preserve alpha at 0.025 for this aim.

In Secondary Aim 2, the safety outcomes of **coagulation and platelet function** each comprise a set of several variables. Noninferiority of HES to albumin will be assessed for each outcome at the 0.025 level using a noninferiority delta of 15% of the mean (as explained above). We will claim noninferiority of HES to standard within a set if noninferiority is shown on all of the variables in a set. Therefore, no adjustment for multiple testing within a set will be done (i.e., intersection-union test).

Safety conclusions will be based on descriptive statistics as well as statistical tests. Multivariate analyses considering a vector or set of related outcomes may also be performed.

For tertiary aims all comparisons will be 2-tailed tests for superiority and analyses will follow the methods outlined below based on type of outcome variable. Each test will be conducted at the 0.05 significance level since these are exploratory analyses.

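### Raw-scale secondary outcomes: if the 15% margin is taken from the observed albumin mean, the test shown runs at about 0.035 or 0.017 per variable, not 0.025

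*Combined protocol and SAP*

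**What the plan says.** All statements are in Statistical Methods of the combined protocol and SAP.

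- **Level.** In the Type I error paragraph: "The significance level will be 0.025 for the 1-tailed noninferiority tests for the primary outcome and for each set of the secondary outcomes". In the Secondary Aim 2 paragraph: "Noninferiority of HES to albumin will be assessed for each outcome at the 0.025 level using a noninferiority delta of 15% of the mean". That sentence refers back to an earlier explanation of the margin. A set passes only if every variable in it passes, with no multiplicity adjustment inside the set.
- **Margin.** The only earlier explanation that says whose mean is meant is the one for NGAL. There the margin is a ratio of geometric means of 1.15, "for an effective delta of 15% of the control group mean". For IL-18 in Secondary Aim 1 the plan specifies a test "using a noninferiority delta of 15% of the mean (or a ratio of geometric means of 1.15, if data are found to be log-normally distributed". That aim also carries this sentence: "A Bonferroni correction will be made to preserve alpha at 0.025 for this aim".
- **Scale.** The rule, for NGAL and the rest alike, is: "if the data are non-normal, a log-transformation will be attempted and the treatment effect (if normal on the log-scale) will be summarized as the ratio". The ratio meant is that of geometric means. Outcomes judged normal therefore stay on the raw scale.
- **Statistic.** One statistic is shown, (β̂1 + δ)/SE(β̂1), where β̂1 "is the estimated treatment effect with standard error" SE(β̂1) "and noninferiority delta of δ". It contains no term for uncertainty in δ.

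No secondary continuous outcome has a numeric margin, a reference mean or a stated harmful direction.

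**The concern.** On the log scale a 15% margin is the constant ln(1.15), and the statistic is sound. On the raw scale, 15% of a mean is a constant only if the mean is fixed in advance. If the mean is the one observed in the albumin arm, δ is a random multiple of a quantity that is already part of β̂1. The variance of the numerator then differs from SE(β̂1)², and by an amount that depends on which direction is harmful.

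Where harm raises the value (taken here to be PT, aPTT, R and K), the test is too lenient, which is the wrong direction for a safety claim. Where harm lowers it (angle, MA, platelet count, aggregation), the test is too strict and loses power, and the all-must-pass rule makes each such loss count. The argument that the intersection-union rule needs no adjustment also assumes that each component test holds its 0.025 level.

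**Working it through.** **Inputs.** From the plan: one-sided 0.025 per Aim 2 variable; a 15% margin; SE(β̂1) as the only denominator; equal groups; at most 130 patients, so 65 per arm. Assumed: the observed albumin mean supplies δ, variances are equal in the two arms, and the harmful directions are as listed above. δ takes the sign that suits each direction.

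**1. The plan's own figure.** With δ a fixed number, the size at the margin is 1 − Φ(1.96) = 0.0250. Simulated t-tests at 52 and 65 per arm gave 0.0247 to 0.0253. The stated level is reproduced.

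**2. δ = 0.15 × observed albumin mean.** With s² the variance and n the number per arm:

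- Higher is worse: the numerator is mean(HES) − 1.15 × mean(ALB). Its variance is (1 + 1.15²)s²/n = 2.3225 s²/n.
- Lower is worse: the numerator is mean(HES) − 0.85 × mean(ALB). Its variance is (1 + 0.85²)s²/n = 1.7225 s²/n.
- The test uses 2s²/n in both cases, so the variance ratios are 2.3225/2 = 1.16125 and 1.7225/2 = 0.86125.

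Size = 1 − Φ(1.96/√ratio):

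- Higher is worse: 1 − Φ(1.96/√1.16125) = **0.0345**
- Lower is worse: 1 − Φ(1.96/√0.86125) = **0.0173**

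Neither n nor the CV appears, so a larger trial does not remove the error. Simulation gave 0.0341 to 0.0343 and 0.0174 to 0.0178 for the t-test. For a baseline-adjusted average of two post-baseline times it gave 0.034 to 0.035 and 0.017 to 0.018.

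**3. Sensitivity.**

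| Assumption | Higher is worse | Lower is worse |
|---|---|---|
| SD proportional to the mean | 0.0331 | 0.0162 |
| Baseline correlation 0.7, unadjusted albumin mean | 0.0351 | 0.0179 |
| Baseline correlation 0.9, unadjusted albumin mean | 0.0373 | 0.0199 |
| 15% of the pooled mean | 0.0253 | 0.0253 |
| Externally fixed mean | 0.0250 | 0.0250 |

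**4. IL-18 on the raw scale.** If Bonferroni splits 0.025 equally over IL-18 and RIFLE, the nominal level is 0.0125. The same ratio of 1.16125 gives about 0.0188.

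**5. Single contrast with its own standard error.** Simulated size returns to 0.0247 to 0.0253 in both directions.

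**6. Power example.** Take 65 per arm, CV 25% (assumed for these outcomes), no baseline adjustment and true equality, in units of the albumin mean. SE(β̂1) = 0.25 × √(2/65) = 0.0439. The standard deviations of the numerators are 0.25 × √(2.3225/65) = 0.0473 and 0.25 × √(1.7225/65) = 0.0407.

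- Higher is worse: Φ((0.15 − 1.96 × 0.0439)/0.0473) = 91.2% with the plan's denominator; Φ(0.15/0.0473 − 1.96) = 88.8% with the contrast.
- Lower is worse: Φ((0.15 − 1.96 × 0.0439)/0.0407) = 94.2% with the plan's denominator; Φ(0.15/0.0407 − 1.96) = 95.8% with the contrast.

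**The case against.** The strongest reply is that the premise is inferred. The phrase that names the control mean describes the NGAL margin, where the problem cannot arise. For the raw-scale outcomes the plan does not say whether the mean is observed, pooled, baseline or external, and the choice decides the result. This stands as a limit. It does not remove the point, because the Aim 2 text refers back to that explanation, no number or outside mean is offered, and the one statistic shown has no variance for δ. The plan cites a methods paper for its tests. Whether that paper covers a margin based on an estimated mean cannot be checked from the documents.

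A reader might infer that the 0.025 level fails throughout the secondary aims. The documents do not support that:

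- **Set level.** The claim is made per set, and all variables must pass. For the coagulation set 0.035 is a worst case, reached when one higher-is-worse variable sits at its margin and the rest pass easily. A set with only lower-is-worse variables, as the platelet set appears to be, is conservative and stays below 0.025.
- **IL-18.** It is tested under Bonferroni, so the 0.035 figure does not apply to it.
- **Scale.** The plan allows transformation of any continuous outcome to meet model assumptions. Outcomes analysed on the log scale are unaffected, and nothing shows how many would stay raw.
- **Weight.** Only NGAL is confirmatory. Safety conclusions also rest on descriptive statistics, and estimates with confidence intervals are to be emphasised.

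These points limit the size of the problem. They do not make the raw-scale test valid at its stated level when the observed albumin mean is used.

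**Conclusion.** The point holds conditionally. If the observed albumin mean defines δ and the statistic is used as shown, each raw-scale Aim 2 variable is tested at about 0.035 where higher is worse and about 0.017 where lower is worse, against a stated 0.025. This assumes equal arms and similar variances. The harmful directions are also assumed, since the plan does not list them. With a pooled or externally fixed mean there is no material error, but the plan would have to say that this is what it means.

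A reader might also infer that the primary analysis is affected. It is not: the NGAL margin is a constant ratio on the log scale. The consequence is modest, confined to raw-scale secondary outcomes, and worth correcting because the lenient side falls on coagulation safety.

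**What to change.** In the Secondary Aim 1 and 2 paragraphs of Statistical Methods:

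1. State that δ refers to the albumin mean, and give the harmful direction of every continuous variable, including LY30.
2. For each outcome analysed on the raw scale, replace the statistic with one linear contrast of model-adjusted means, evaluated at the overall mean of the covariates and divided by its own standard error. Noninferiority requires mean(HES) − 1.15 × mean(ALB) < 0 where higher is worse, and mean(HES) − 0.85 × mean(ALB) > 0 where lower is worse. Each is tested one-sided at the level set for that outcome.
3. Alternatively, analyse strictly positive variables on the log scale with a constant ratio margin, which the plan already provides for when data are non-normal.

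The cost is a short text change and one contrast statement per outcome, with no added patients. In the example above, higher-is-worse variables lose about 2 points of power (91.2% to 88.8%) and lower-is-worse variables gain about 1.6 (94.2% to 95.8%).

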The randomized HES and standard therapy groups will be descriptively compared for balance on potentially confounding baseline variables (including duration of cardiopulmonary bypass, use of anti-fibrinolytic therapy, preoperative anticoagulant medications, including clopidogrel). Any baseline variable for which the standardized difference (i.e., observed difference in means or proportions divided by the pooled standard deviation of the outcome) is greater than 0.25 will be considered imbalanced and adjusted for as a covariate in each of the below analyses. We will not use P-values to determine baseline imbalance since the P-value is quite dependent on the sample size, whereas the standardized difference is more independent of sample size and thus a better assessment of balance. [A standardized difference of 0.25 is conservative (should be 0.39) based on the expected 2.5th and 97.5th percentiles of the sampling distribution, i.e., $1.96 \times \sqrt{2/n}$ per group = 50 = 0.39.]³⁰ For all analyses of continuous variables, transformations of the data will be made as appropriate to achieve normality and/or meet other model assumptions. If transformations are not successful, non-parametric analyses analogous to those described below will be employed. For example, we might employ a Wilcoxon rank-sum test to compare the groups on IL-6 at a particular time point if the data are not close to a normal or log-normal distribution.

All primary analyses will be modified intent-to-treat (M-ITT), such that the groups being compared will be all patients who are randomized and who undergo surgery. Analyses of the safety outcomes in Aims 1 and 2 will be noninferiority assessments, and so 1-tailed. All tertiary analyses will be 2-tailed tests for superiority. Conclusions about the effect of HES will be confirmatory for the primary outcome (urinary NGAL) and more exploratory for other outcomes. We will also conduct a “per protocol” analysis for the primary outcome and describe whether these results differ from the modified intent-to-treat results. In the per-protocol analysis we will analyze patients according to the treatment received as oppose to the randomized treatment, and only those patients who complete the entire trial according to the protocol will be included. In case of a discrepancy, the M-ITT results will be primary.

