Continuous outcomes measured over time (Primary and secondary aims). For the primary outcome (urinary NGAL) and each of the secondary continuous outcomes which are measured over time (e.g., at baseline, within one hour of arrival to ICU following surgery, and 24 hours following completion of surgery), we will assess the treatment effect of HES 130/0.4 versus standard care using linear mixed effects models (with patient as random effect), adjusting for the baseline value of the outcome and any baseline variables for which balance among the randomized groups was not achieved through randomization. We will adjust for the baseline value of the outcome for efficiency, i.e., to obtain a smaller standard error for the estimate of treatment effect to the extent that the baseline value is correlated with the later time points, regardless of baseline balance. An unstructured within-subject correlation structure will be employed, estimating a distinct correlation parameter for each pair of post-baseline measurement times.

If the treatment group-by-time interaction is significant ($P < 0.15$), the treatment effect for a particular outcome will be assessed at each of the post-baseline time points measured, using a Bonferroni (or other appropriate) correction for multiple comparisons procedure if comparing groups at specific time points. Similarly, correction to the significance criterion will be made in all analyses below when comparing multiple times, as appropriate.

Ordinal outcome. Groups will be compared on the ordinal outcome of the RIFLE criteria (Secondary Aim 1) using proportional odds logistic regression, adjusting for baseline imbalance

as needed. We will assess noninferiority using the approach described above for the primary outcome, where $\hat{\beta}_1$ is the estimated treatment effect in the form of a log-odds ratio.

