Interim monitoring analyses. We will conduct interim analyses for the parameter urinary NGAL (assessing safety [i.e., noninferiority] and non-safety [i.e., noninferiority not found]) at every 1/6th (16.7%) of the maximum enrollment of 130 patients, or approximately at every 22 or 23 patients, in a group sequential design. We will use the gamma spending function with gamma of -5 for safety (alpha spending; very conservative, like O-Brien-Fleming boundaries) and gamma of 0 for futility, or non-safety (beta spending; fairly aggressive, like Pocock boundaries). We spend the beta faster than the alpha in order to be able to detect any potential harm of the treatment as early as possible in the trial. Table 3 gives the P-value boundaries for efficacy and futility at each interim look (columns 5 and 6). Column 2 gives the total sample size at each look. The last 2 columns give the probability of crossing a boundary when the null hypothesis is true (Under H0) and when the alternative (noninferiority) is true (H1). For example, if Voluven is truly noninferior, the probability of crossing the safety boundary is 3.1% at the first look, $3.1\% + 12.7\% = 16\%$ through the second look, and so on. The below figure displays the boundaries on the z-scale (A) and the error spending functions (B) for this design.

Table 3. Interim Monitoring -- Group Sequential Design Boundaries							
Information action	Cumulative Accrual	Alpha Spent	Beta Spent	P-value Boundaries		Boundary Crossing Probabilities	
				Safety H0	Non-safety H1	Under H0 For nonsafety	Under H1 For safety
0.167	22	0.0004	0.017	<0.001	0.746	0.254	0.031
0.333	43	0.001	0.033	0.001	0.471	0.303	0.127
0.500	65	0.003	0.050	0.002	0.256	0.217	0.229
0.667	86	0.006	0.067	0.005	0.125	0.122	0.252
0.833	108	0.013	0.083	0.010	0.056	0.060	0.183
1.000	130	0.025	0.100	0.021	0.021	0.025	0.078

A. Z-statistic Stopping boundaries

B. Alpha and beta spending functions

Sample size calculations (Aim 1):

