Sample size is based on assessing the noninferiority of HES 130/0.4 to 5% albumin on the primary outcome of urinary NGAL. In patients undergoing cardiac surgery, Koyner et al (2012)²⁹ observed median [quartile] urinary NGAL values of 28.3 (13.5–82.9) in patients who did not progress to renal failure and 72.1 (11.4–495.6) in patients who progressed to renal failure. Assuming that NGAL values follow a log-normal distribution as in previous studies, we can use the above observed quartiles to estimate the mean, standard deviation and coefficient of variation (CV) for the above groups, yielding CV of 2.3% and 50%, respectively. Assuming for the current study a coefficient of variation between these values, or 25%, we would need 52 patients per group (total of 104) to have 90% power at the 0.025 significance level to be able to claim noninferiority of HES to albumin using a noninferiority delta of a ratio of geometric means of 1.15. These calculations assume no treatment-time interaction and therefore no Bonferroni correction for comparing groups at each of two time points within an outcome. Based on the above calculations, a sample size of 110 would suffice for a study with no interim monitoring. **Adjusting for the interim monitoring at each one-sixth of the total, a maximum sample size of 130 patients are required. Allowing for 5 potential dropouts and 5 pilot patients (which will not be included in the analyses), we will plan for a potential total of 140 patients.**

STUDY PROCEDURES

Quality Assurance

The major components of quality assurance will be staff training, the standardization of data collection, entry, and processing, and ongoing monitoring to ensure timeliness and accuracy of study data. All study protocols and forms will be compiled into two operations manuals (one for the clinical sites and one for data management) that will be revised as necessary. A clinical reference manual will be created and will include administration and scoring criteria, specific testing instructions and inclusion and exclusion criteria for diagnosis and study ascertainment. This manual will also contain copies of test forms and will be available to all study personnel from a password-protected web site. The current manual for data management will be made easily available to data management personnel and used for continued training. This manual will include a question-by-question written script for interviewing purposes.

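### If the group-by-time interaction is significant, does the missing one-time-or-both pass rule undermine the primary NGAL claim?

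*Combined protocol and SAP*

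**What the plan says.** All of this is in the combined protocol and SAP, mostly under Statistical Methods.

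- Status of the outcome: conclusions are "confirmatory for the primary outcome (urinary NGAL) and more exploratory for other outcomes".
- Type I error: "The significance level will be 0.025 for the 1-tailed noninferiority tests for the primary outcome". The margin is a ratio of geometric means of 1.15.
- Primary hypothesis: the effect is estimated in a linear mixed model across the collapsed times if there is no interaction, "or else at specific times if there is an interaction detected".
- Continuous outcomes measured over time: the interaction threshold is P < 0.15. Beyond it, the effect "will be assessed at each of the post-baseline time points measured, using a Bonferroni (or other appropriate) correction".
- Secondary Aim 2 is the only place with an all-must-pass rule: "We will claim noninferiority of HES to standard within a set if noninferiority is shown on all of the variables in a set". The plan adds that such a rule needs no multiplicity adjustment.
- Interim monitoring: "We will conduct interim analyses for the parameter urinary NGAL", at six looks. Whether this is the averaged or a time-specific ratio is not stated.
- Sample size: "These calculations assume no treatment-time interaction and therefore no Bonferroni correction for comparing groups at each of two time points within an outcome".

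**The concern.** NGAL carries the only confirmatory claim, and the interaction branch is entered exactly when the data suggest that the effect differs between ICU arrival and 24 hours. With no written rule, a pass at one time might be presented as noninferiority on NGAL while the other time is truly beyond 1.15. The choice could also be made after seeing which time passed.

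The text leans both ways. The hypothesis names both times, which suggests that both must pass. But a Bonferroni split is needed only if either time can support a conclusion of its own, as the Secondary Aim 2 logic implies. The interim section adds to the doubt because it does not say which ratio the Table 3 boundaries monitor, or whether the interaction test is applied at each look.

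**Working it through.** **Inputs from the plan.** Margin ln 1.15 = 0.1398. CV 25%, so log SD = √ln(1 + 0.25²) = 0.2462. Maximum 130 patients, 65 per group. One-sided 0.025, or 0.0125 per time after the split (z = 2.241). Interaction threshold two-sided 0.15 (z = 1.440). **Assumed, because the plan gives no value:** correlation between times of 0.3, 0.5 or 0.7. Triplets below are in that order.

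**The plan's own figures.** Table 3 is consistent with 90% power: 0.031 + 0.127 + 0.229 + 0.252 + 0.183 + 0.078 = 0.900. The stated 52 per group is not reproduced for a single time: 2(1.960 + 1.282)² × 0.2462² / 0.1398² gives 66. For the mean of two times this is multiplied by (1 + correlation)/2, giving 49 at correlation 0.5 and 53 at 0.6. That is a separate matter; the checks below use the 130 maximum.

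**Where the 83% comes from (true ratios 1.2 and 1.0, single final look).**

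1. SE of one log ratio: 0.2462 × √(2/65) = 0.0432.
2. Time with ratio 1.00: Φ(0.1398/0.0432 − 2.241) = Φ(0.995) = 84.0%; the exact t calculation gives 83.2%.
3. Time with ratio 1.20: Φ((0.1398 − 0.1823)/0.0432 − 2.241) = Φ(−3.23), about 0.06%.
4. Interaction test at correlation 0.5: the SE of the difference is 0.0432 × √(2 × 0.5) = 0.0432, so it is significant with probability of about Φ(0.1823/0.0432 − 1.440) = Φ(2.78) = 99.7%.

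So the 83% is the chance of a correct finding at the unaffected time.

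**Comparison with the averaged hypothesis.** The geometric mean of 1.2 and 1.0 is √1.2 = 1.095, inside the margin. At correlation 0.5 the SE of the average is 0.0432 × √0.75 = 0.0374, so the averaged test alone passes with probability Φ((0.1398 − 0.0912)/0.0374 − 1.960) = Φ(−0.66), about 25%. Group-sequential simulation gives 28/25/22%. For 1.2 and 1.1 the geometric mean is √1.32 = 1.149, also inside.

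**Group-sequential simulation** (Table 3 boundaries, interaction test applied at each look, both of which are assumptions about the unstated detail; either-time rule with split, both-times rule without it):

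| True ratios, setting | Either time passes | Both times needed |
|---|---|---|
| 1.2 and 1.0, CV 25%, non-safety stopping ignored | 83/83/83% | 1.7/0.7/0.3% |
| Same, non-safety stopping on the average followed | 45/43/41% | – |
| 1.2 and 1.0, log SD 1.35 | 7.2/6.6/6.0% | 3.6/3.3/3.0% |
| 1.2 and 1.1, CV 25% | 11.6/11.3/11.2% | 1.3/1.0/0.6% |
| 1.15 and 1.15, non-safety stopping ignored | 3.6/3.3/3.0% | about 2.2% |
| Same, non-safety stopping followed | 2.5/2.4/2.3% | – |

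The log SD of 1.35 is ln(82.9/13.5)/1.349, from the quartiles in the sample size section. Under a different convention for non-safety stopping (twice the smaller P value compared with each boundary), the first row becomes about 68–71%.

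**What a both-times rule would cost (CV 25%, unsplit, non-safety stopping ignored).** At equality, power is 93.8/92.3/90.6% against 97.7/95.9/93.4% for the averaged test. At 1.05 and 0.95 it is 67/62/57% against 98/96/94%. It does not close every gap either: through the averaged branch it still passes in 11.6/8.0/4.6% of trials at 1.15 and 1.05.

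**The case for a change.** The strongest case for acting is that the omission sits in the one confirmatory test of a safety trial, that the plan states an explicit rule for Secondary Aim 2 but not here, and that one sentence with no added patients would settle it. A sponsor who prefers the either-time reading should still limit the claim to that time. The interim section makes things less clear, and it signals that the non-safety boundary is meant to be acted on: "We spend the beta faster than the alpha in order to be able to detect any potential harm of the treatment".

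Part of this stands. No section states the pass rule, and an overall claim built on one passing time would mislead. There is also a small excess error when both ratios sit at 1.15: 3.0–3.6% against 2.5%, at most 1.1 points, and none if non-safety stopping is followed.

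The rest does not carry through to a change. Assessing each time at a split level normally means two separate conclusions, and Bonferroni is the right correction for that. Ratios of 1.2 and 1.0 would then usually be reported as noninferior at one time and not shown at the other, which is true. The plan also promises confidence intervals for all analyses and puts them, with the point estimates, at the front of its reporting, so the adverse time could not easily drop out of sight. The Executive Committee section says interim analyses are programmed in advance, and the sizing assumes no interaction, so the averaged ratio is the natural reading of Table 3.

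**Conclusion.** This is an unwritten detail, not a demonstrated error. Following the text gives Bonferroni-corrected, time-specific conclusions when the interaction is significant, and these are sound provided each is reported for its own time. The 83% would describe a misleading claim only if a single pass were relabelled as overall noninferiority. It also rests on CV 25%, a ratio of exactly 1.00 at the other time, a maximum of 130 patients and non-safety stopping being ignored. It falls to 41–45% when stopping on the averaged ratio is followed, and to 6–7% at log SD 1.35.

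Requiring both times would swap one set of operating characteristics for another: fewer passes when one time is harmed, but roughly 31–37 points less power than the averaged test at 1.05 and 0.95 (98 − 67, 94 − 57), and still up to about 12% passing with one time at the margin. Either rule is defensible. No change to the plan follows.
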